4.2.2.5 Additional Analyses of Secondary Endpoint

No additional analysis.

4.2.2.6 Subgroup Analyses of Secondary Endpoint

The analysis described in Section 4.2.2.4 is repeated in subgroups described in Section 4.2.1.7.

4.2.2.7 Interim Analysis of Secondary Endpoint

No presentation for interim analysis.

4.2.3 Secondary Endpoint - Rate of asthma exacerbation associated with hospitalisation over 28 weeks and over 28 weeks and 52 weeks

4.2.3.1 Definition

Two rates of asthma exacerbation are assessed:

- Annualized rate of asthma exacerbation associated with hospitalisation or emergency room (ER) visit over 28 weeks and over 52 weeks.
- Annualized rate of asthma exacerbation associated with hospitalisation over 28 weeks and over 52 weeks.

Exacerbations due to hospitalisations or ER visits and exacerbations associated with the hospitalisations are a subset of all asthma exacerbations.

4.2.3.2 **Derivations**

Both endpoints are similarly derived to AAER including all asthma exacerbations as described in Section 4.2.2.2 but based on the selected asthma exacerbations, i.e., associated with hospitalisation or emergency room (ER) visit or associated with hospitalisation only.

4.2.3.3 Handling of Dropouts and Missing Data

No data imputation.

4.2.3.4 Primary Analysis of Secondary Endpoint

The same analysis as described in Section 4.2.2.4 is presented but including exacerbations associated with hospitalisation or emergency room (ER) or with hospitalisation only. The analyses are performed based on the FAS.

4.2.3.5 Additional Analyses of Secondary Endpoint

No additional analysis.

4.2.3.6 Subgroup Analyses of Secondary Endpoint

The analysis described in Section 4.2.3.4 is repeated in subgroups described in Section 4.2.1.7.

4.2.3.7 Interim Analysis of Secondary Endpoint

No presentation for interim analysis.

4.2.4 Secondary Endpoint - Proportion of participants who did not experience an exacerbation at Week 28 and Week 52.

4.2.4.1 Definition

There are three proportions to assess this secondary endpoint:

- Proportion of participants who did not experience an exacerbation,
- Proportion of participants who did not experience an exacerbation associated with hospitalization or ER visit,
- Proportion of participants who did not experience an exacerbation associated with hospitalization.
- Each of those proportion of participants (i.e., who did not experience an exacerbation; an exacerbation associated with hospitalization or ER visit; an exacerbation associated with hospitalization only) are calculated over 28 weeks and over the 52-week period.

4.2.4.2 **Derivations**

For considering a participant without any experience of exacerbation, the planned treatment period defined in Section 3.3.1.1 has to be considered. A participant is considered to have completed the planned treatment period, if the planned treatment period is greater than

- than 191 (Day 196 minus 5) for the analysis at Week 28
- 359 days (Day 364 minus 5, to account for visit windowing) for the analysis at Week 52

Participants who had no asthma exacerbations during the planned treatment period and who completed the period of interest (up to Week 28 or Week 52) without initiating another biologic are defined as exacerbation free/successful outcome [a].

Participants who did not complete the planned treatment period or initiate another biologic during the planned treatment period are defined as not having a successful outcome for this endpoint [b] [c].

Participants who completed the planned treatment period without initiating another biologic and had an asthma exacerbation are defined as not having a successful outcome for this endpoint [d].

	No asthma exacerbation	Asthma exacerbation
Completed planned treatment period without initiating another biologic	[a] Exacerbation free/successful outcome	[d] No successful outcome
Did not complete treatment period or initiate another biologic during the planned treatment period	[b] No successful outcome	[c] No successful outcome

The proportion is calculated as the number of participants with a successful outcome at Week 28/Week 52 divided by total number of participants in the FAS population.

The proportion of participants free from exacerbations that required hospitalisation or ER visits (or hospitalization only) during the planned treatment period is calculated similarly. A participant who only had an exacerbation which did not lead to hospitalisation or ER visit (or hospitalisation only) is considered a successful outcome for this endpoint.

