At the IPD Visit the participants will be given the following 3 options as to how they will be followed:

- 1. The participant should be encouraged to return for all regular clinic visits and perform all scheduled assessments (excluding IP administration) until the EOT visit at Week 52 (± 5 days).
- 2. The participant will be offered follow-up on a monthly basis via telephone calls while continuing ePRO data collection on the handheld device at home (no further procedure will be performed) until the participant completes the on-site EOT visit at Week 52 (± 5 days).
- 3. If the participant cannot or does not wish to comply with any of the options above (or any component of them such as only telephone-based visits without completion of the ePRO data), the investigator will contact the participant via telephone at 52 weeks after baseline. No other study assessments will be performed prior to this contact.

Participants who discontinue IP with option 1 or 2 are allowed to further reduce their OCS dose following the same protocol-specified OCS dose reductions scheme as participants being still on-treatment.

If the last study intervention administration was after Week 36 for options 1 or 2, the participant will return to the clinic for an EOT visit at Week 52 (\pm 5 days). For option 3, the investigator will contact the participant at 52 weeks post baseline.

If a participant chooses option 1, all assessments will be completed as per the SoA as indicated in Table 1. If a participant chooses option 2 or 3, the key information to be collected during the telephone calls are AESIs/DAEs/SAEs, changes in concomitant medication, and asthma exacerbation information.

Participants who initially choose options 1 or 2 and subsequently cannot or do not wish to comply with the requirements of their option can continue with a less intensive option

(ie, participants initially choosing option 1 can continue with options 2 or 3, participants initially choosing option 2 can continue with option 3).

If a participant discontinues tezepelumab due to a study specific discontinuation criterion, this should always be recorded as 'Development of study specific discontinuation criteria' on the Discontinuation of IP form in the eCRF.

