7.3 Lost to Follow-up

A participant will be considered lost to follow-up if he/she repeatedly fails to return for scheduled visits and is unable to be contacted by the study site.

The following actions must be taken if a participant fails to return to the clinic for a required

study visit:

- The site must attempt to contact the participant and reschedule the missed visit as soon as possible and counsel the participant on the importance of maintaining the assigned visit schedule and ascertain whether or not the participant wishes to and/or should continue in the study.
- Before a participant is deemed lost to follow-up, the investigator or designee must make
 every effort to regain contact with the participant (where possible, 3 telephone calls and,
 if necessary, a certified letter to the participant's last known mailing address or local
 equivalent methods). These contact attempts should be documented in the participant's
 medical record.
- Should the participant continue to be unreachable, he/she will be considered to have withdrawn from the study.

Discontinuation of specific sites or of the study as a whole are handled as part of Appendix A.

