3.3.1 General Study Level Definitions

3.3.1.1 Study period definition

Efficacy analyses are based on planned treatment period, unless otherwise specified. Safety analyses are based on-treatment and/or on-study period.

- Planned treatment period: starts on the date of first dose of IP and ends on the date of the Visit 15 (Week 52) visit or earlier study withdrawal date.
- On-treatment period: starts on date of first dose of IP and ends on earliest(date of last dose of IP + 33 days, date of death, date of study withdrawal). The date of study withdrawal is the completion or discontinuation date from the DISPOSITION eCRF page, where any participant status other than "Completed" has been entered.
- On-study period (planned treatment period and follow-up): starts on the date of first dose of IP and ends on the study completion or withdrawal date.

For analysis performed at primary database lock, the planned treatment period is understood to include all data recorded starting on the date of first dose of IP up until the date of the data cut-off for the primary database lock (details regarding the DCO date and data cleaning can be found in Data Cleaning Requirements for Primary Analysis Lock Plan).

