Two or more exacerbations with the same start date and end date are counted as one exacerbation for the purposes of calculating the number and duration of exacerbations for a participant. In the case that one or more exacerbations are recorded as starting or ending during another exacerbation, these is counted as one exacerbation, using the earliest exacerbation start date and the latest exacerbation stop date to calculate duration.

Additional systemic corticosteroid treatments, emergency room or urgent care visits requiring use of systemic corticosteroids, or inpatient hospitalisation due to asthma occurring during an exacerbation is not regarded as a new exacerbation. To be counted as a new exacerbation it must be preceded by at least 7 days in which neither criterion is fulfilled. If the end date of the first exacerbation or a temporary increase in a stable OCS background dose date, date of ER or urgent care visit, or date of hospital discharge and the start date of the second exacerbation are less than 7 days apart, then these is counted as one exacerbation.

It should be noted that the date of last assessment of exacerbation status from the eCRF might be later than the last available visit during the planned treatment period, in the case that the participant remained in the study with incomplete follow-up options after early discontinuation of IP.

The exacerbations that occur after a participant has discontinued IP but before the end of the time at risk is still accounted when deriving the total number of exacerbations.

^b 7 days should be added to each asthma exacerbation duration as no asthma exacerbation can occur during that time.

Likewise, the time at risk reflects the time at risk regardless of whether the participant is still on IP or not.

Any exacerbations that start within the time at risk but ends after this time point is included in analyses, with the end date adjusted to be no later than the time at risk. Any exacerbation that starts after the time at risk is not included in analyses.

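### SAP 4.2.4.2 counts the exacerbation-free period as completed on calendar length alone, so a few participants who stopped IP early can be scored as Week 28 successes without having been assessed to Week 28

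*SAP*

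**What the plan says.** SAP 4.2.4.2 scores a participant as exacerbation-free (cell [a]) under three conditions: no exacerbation, period completed, no other biologic started. The text begins: "Participants who had no asthma exacerbations during the planned treatment period and who completed the period of interest". Completion is a matter of length only: "A participant is considered to have completed the planned treatment period, if the planned treatment period is greater than" the threshold, which is "than 191 (Day 196 minus 5) for the analysis at Week 28" and "359 days (Day 364 minus 5, to account for visit windowing) for the analysis at Week 52". Anyone who did not complete, even with no event, is not a success (cells [b] and [c]). The denominator is the FAS, and SAP 4.2.4.3 plans no imputation.

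SAP 3.3.1.1 says the planned treatment period "ends on the date of the Visit 15 (Week 52) visit or earlier study withdrawal date". At the primary lock it runs to the data cut-off. Stopping IP does not shorten it.

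Protocol 7.1 gives participants who stop IP three follow-up options. Options 1 and 2 keep at least monthly contact. Option 3 is one telephone call at Week 52, and "No other study assessments will be performed prior to this contact". The same section also says that everyone who stops IP early should have a follow-up 16 weeks after the last dose. Table 1 marks exacerbation assessment at both the IPD visit and that follow-up.

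**The concern.** Length of time in the study is not the same as observation for exacerbations. A participant on option 3 has not withdrawn, so the planned treatment period keeps running while no one asks about exacerbations. With nothing recorded, the rule returns a success.

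The SAP recognises this situation for the AAER. It notes that "the date of last assessment of exacerbation status from the eCRF might be later than the last available visit" for participants with incomplete follow-up after stopping IP. When Visit 9 is missing, Table 5 ends time at risk no later than the latest of the last visit, death and the EXACD status date. The same person therefore stops contributing time to the rate at the last assessment but counts as a full-period success in the proportion.

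The rule also treats similar people differently. Formal withdrawal at Week 12 without an event is a failure under [b]. Stopping IP and choosing option 3 at Week 12 can be a success, with no more information about Weeks 12 to 28.

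Compared with requiring assessment, the rule can only raise the reported proportion, and this single-arm study has no control arm to offset that. The proportions are repeated in subgroups (SAP 4.2.4.6). In the low-eosinophil stratum planned at 10% of 300 = 30 participants, one reclassified participant moves the result by 1/30 = 3.3 points.

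**Working it through.** **The plan's own figures.** The thresholds reproduce: 28 × 7 − 5 = 191 and 52 × 7 − 5 = 359. The stated precision (SAP 1.3) also reproduces: Clopper-Pearson for 150/300, with lower limit the 2.5% quantile of Beta(150, 151) and upper limit the 97.5% quantile of Beta(151, 150), gives 50% ± 5.8 points.

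**Unassessed time before Week 28 on option 3.** Inputs: IPD visit 4 weeks after last dose and follow-up contact 16 weeks after last dose (protocol 7.1), visit windows ignored. For last dose at week w, the gap is 196 − 7(w + 4) days without the 16-week contact and 196 − 7(w + 16) with it, floored at zero.

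| Last dose (week) | IPD (days from first dose) | Gap, no 16-week contact | Gap, contact made |
|---|---|---|---|
| 0 | 28 | 168 | 84 |
| 4 | 56 | 140 | 56 |
| 8 | 84 | 112 | 28 |
| 12 | 112 | 84 | 0 |
| 16 | 140 | 56 | 0 |
| 20 | 168 | 28 | 0 |
| 24 | 196 | 0 | 0 |

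In every row the planned treatment period exceeds 191 days at the primary lock if the participant has been in the study that long and has not withdrawn. With nothing recorded and no other biologic, the result is [a].

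**Week 52.** The option 3 call collects exacerbation information, so a completed call closes the gap. If it fails, protocol 7.3 applies: "Should the participant continue to be unreachable, he/she will be considered to have withdrawn from the study". If that withdrawal is dated after Day 359, the participant is still a success. A participant with neither a Visit 15 nor a withdrawal date has no defined end of period in SAP 3.3.1.1, and the result depends on programming.

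**Size.** The documents give no count, so these are assumptions: 5-10% of 300 stop IP before Week 28, and 20-40% of them take option 3.
- Without the 16-week contact: 300 × 0.05 × 0.20 = 3 to 300 × 0.10 × 0.40 = 12 participants, or 1.0 to 4.0 points. This is a ceiling, because it counts every stop before Week 28 and supposes no recorded event and no other biologic.
- With the contact, and last doses spread evenly over the seven visits from Week 0 to Week 24, 3/7 are exposed: 3 × 3/7 = 1.3 to 12 × 3/7 = 5.1 participants, or 0.4 to 1.7 points.

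These are participants reclassified by the fix. The bias is only the share who exacerbated in the gap. Assuming 1 to 2 exacerbations per year, 1 − exp(−rate × gap/365.25) gives 7% (rate 1, 28 days) to 37% (rate 2, 84 days). With the contact made, the largest bias is 5.1 × 0.37 = 1.9 participants, or 0.6 points.

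As an illustration, suppose 6 of 300 are unassessed and 60% of the other 294 are event-free (176). The SAP rule gives 182/300 = 60.7% (95% CI 54.9 to 66.2). Requiring assessment gives 176/300 = 58.7% (52.9 to 64.3).

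**The case against.** A reader might infer that no one on option 3 is assessed between the IPD visit and Week 52, and that all six proportions (three types at two time points) are inflated alike. The documents support neither reading.

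- The 16-week follow-up is stated for all who stop IP. If it is made, a last dose at Week 8 leaves about 28 unassessed days, not 16 weeks, and a last dose at Week 12 or later leaves none. This stands as a limit on scope. It does not remove the problem, because the option 3 text, and footnote m to Table 1, describe the Week 52 call as the only further contact.
- At Week 52 the call collects the missing information. No rule dates the withdrawal of someone who cannot be reached, and a failed 16-week contact could start tracing, and so withdrawal, much earlier. The Week 52 effect is therefore narrow.
- By the primary lock, participants first dosed at least 24 weeks before the last one may already have had the Week 52 call. Accrual is not given, so this reduces the number exposed by an unknown amount.
- Keeping participants who stopped IP eligible for success follows the treatment-policy strategy. That is right, but the issue is missing assessment, not stopped treatment.
- Classing unassessed participants as failures is a worst-case rule and will misclassify those who were truly event-free. This is a real cost, but the SAP already applies that rule to incomplete follow-up in cell [b].

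**Conclusion.** The gap in SAP 4.2.4.2 is real and follows from the text: completion depends on elapsed time, and no assessment is needed. The clear effect is on the three Week 28 proportions at the primary lock, for option 3 participants with an early last dose (Weeks 0, 4 or 8 if the 16-week contact is made, otherwise any whose IPD visit falls before Day 191). At Week 52 it is confined to failed calls with withdrawal dated after Day 359, and to participants with neither a Visit 15 nor a withdrawal date.

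Under the assumed rates, the number reclassified is at most 3 to 12 of 300, or about 1 to 5 with the contact and evenly spread stops. Both ranges lie below the 5.8-point half-width, and the true bias is smaller again. It would be wrong to read every unassessed participant as a false success. This is a cheap improvement, of minor to moderate severity.

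**What to change.** In SAP 4.2.4.2, add to the completion condition: the last exacerbation-status assessment (EXACD date, or last visit or contact at which exacerbations were assessed) is more than 191 days (Week 28) or 359 days (Week 52) after first dose, counted as for the planned treatment period; otherwise the participant is classed as not completed ([b]/[c]). With an inclusive count, a Visit 9 held five days early (191 days elapsed, length 192) still qualifies, so on-schedule attendees are unaffected. A Week 52 call already in the data at the primary lock would also qualify.

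Separately, reconcile the two statements in protocol 7.1 on whether option 3 participants receive the 16-week follow-up contact.

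The cost is one sentence and a date already needed for Table 5. The reported proportion becomes slightly lower, and some participants who were truly event-free will count as not successful.

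### The exacerbation-free proportions over 28 weeks have no Week 28 stop: SAP 4.2.4.2 counts exacerbations over a period that runs to Visit 15 or the data cut-off

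*SAP*

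**What the plan says.** SAP 4.2.4.1 lists three proportions (no exacerbation; none with hospitalisation or ER visit; none with hospitalisation), which "are calculated over 28 weeks and over the 52-week period". Protocol Section 3, Table 2, gives the same periods.

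SAP 4.2.4.2 then sets the rule. To classify a participant, "the planned treatment period defined in Section 3.3.1.1 has to be considered". The period counts as completed if it is longer than 191 days for Week 28 or 359 days for Week 52. Success [a] goes to "Participants who had no asthma exacerbations during the planned treatment period and who completed the period of interest (up to Week 28 or Week 52", provided no other biologic was started. Outcomes [b] and [c] cover "Participants who did not complete the planned treatment period or initiate another biologic during the planned treatment period". Outcome [d] is a completer with an exacerbation. For the two hospitalisation/ER versions, the proportion "during the planned treatment period is calculated similarly".

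SAP 3.3.1.1 says that the planned treatment period "ends on the date of the Visit 15 (Week 52) visit or earlier study withdrawal date". For the primary database lock it includes all data from first dose "up until the date of the data cut-off for the primary database lock".

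**The concern.** The endpoint is named for 28 weeks, but the period searched for exacerbations has no Week 28 end. SAP 3.1 places the primary lock after about 300 participants have completed 28 weeks, so early entrants will by then have data well beyond Week 28. SAP 4.2.7.4 and several later sections say outright that such data are presented at that lock.

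Read literally, a participant with no exacerbation through Visit 9 and a first one at, say, Week 40 is a Week 28 failure. Observation would range from about 28 weeks for the last entrants to 52 weeks for the earliest. Three secondary endpoints at the primary lock would then not be 28-week proportions. SAP 4.2.4.6 repeats them by subgroup, including region, so groups that enrolled at different times could differ through calendar time alone.

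**Working it through.** **The plan's own figures.** 28 × 7 = 196 and 196 − 5 = 191; 52 × 7 = 364 and 364 − 5 = 359. Both thresholds reproduce. Each is a lower limit on the length of the period, so neither ends the counting. The exact Clopper-Pearson half-width for 150/300 is 5.8 points, as in SAP Table 2.

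**Which words govern what.** In [a], the reference to Week 28 or Week 52 attaches to completion and, through "completed the period of interest (up to Week 28 or Week 52) without initiating another biologic", to the other-biologic condition. The exacerbation condition attaches to the planned treatment period.

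**How related text handles Week 28.**
- Annualised rate (SAP 4.2.2.2, Table 5): 28-week time at risk stops at Visit 9 or, if Visit 9 is missing, no later than first dose + 196 + 5 days. Exacerbations starting later are excluded.
- Time to OCS reduction (SAP 4.2.13.2): participants without the event are censored at Visit 9, or at first dose + 196 days, or at another biologic if earlier.
- Systemic corticosteroid exposure (SAP 4.2.21.2): the planned treatment period is qualified as 28-week or 52-week.
- Protocol 9.4.1: the efficacy period ends at the Week 28 or Week 52 visit.

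SAP 4.2.4 has no such stop and does not refer to Table 5.

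**Illustrative size.** Assumed, because the documents give no values: a constant rate λ per year; uniform accrual over 24, 52 or 78 weeks; cut-off when the last participant reaches Week 28; follow-up capped at 52 weeks; no dropout.

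- Success over t years: exp(−λt) (Poisson) or 1/(1 + λt) (dispersion 1).
- 28 weeks: t = 196/365.25 = 0.5366. 52 weeks: t = 364/365.25 = 0.9966.
- Follow-up as written: min(28 + U, 52) weeks, with U uniform over the accrual period.

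Worked case, λ = 0.4, 52-week accrual, Poisson:
- Intended: exp(−0.4 × 0.5366) = 80.7%.
- Followed 52 weeks: exp(−0.4 × 0.9966) = 67.1%. Share at the cap: 28/52 = 53.8%.
- Average for the remaining 46.2%, followed 28 to 52 weeks: (0.8068 − 0.6712)/(0.4 × 0.4600) = 73.7%.
- As written: 0.462 × 73.7 + 0.538 × 67.1 = 70.2%, a loss of 10.5 points. The exact 95% CI at 242/300 (80.7%) is −4.9/+4.3 points.

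Loss in points for 24 / 52 / 78 weeks' accrual:

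| Rate per year | Poisson | Dispersion 1 |
|---|---|---|
| 0.4 | 7.0 / 10.5 / 11.5 | 5.7 / 8.4 / 9.2 |
| 0.7 | 10.0 / 14.8 / 16.2 | 7.4 / 10.8 / 11.8 |
| 1.0 | 11.6 / 17.0 / 18.5 | 8.1 / 11.8 / 12.9 |
| 0.10 | 2.1 / 3.3 / 3.6 | 2.0 / 3.1 / 3.4 |
| 0.05 | 1.1 / 1.7 / 1.9 | 1.1 / 1.6 / 1.8 |

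Mean follow-up is 40.0, 46.5 and 48.3 weeks instead of 28. If 10% do not complete Week 28, they fail under either reading and each loss is multiplied by 0.9. For the two low rates, the exact CI is −3.1/+2.2 points at 285/300 (95%) and −2.6/+1.6 at 291/300 (97%).

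**The case against.** The best defence is that the intention is plain. The endpoint is defined over 28 weeks. The completion rule treats the period as specific to the analysis. The table row for [a] says planned treatment period where the prose says period of interest, as if the two were the same. SAP 4.2.21.2 and protocol 9.4.1 both give the period a 28-week form, and SAP Section 2 declares no difference from the protocol. A careful programmer could well stop at Week 28. All of that stands as evidence of intent. It does not supply the missing stop in the operative rule, which points to a section whose end date is later.

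The illustration is also fairly challenged. Rate, dispersion, accrual and cut-off are all assumed, and enrolment may have been slow at first. In a back-loaded case (50 participants already at 52 weeks, 250 entering evenly over 24 weeks) the Poisson loss is 8.1 points at 0.4 per year and 13.3 at 1.0. That is smaller than under long uniform accrual but still larger than the interval half-width.

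Two stronger readings are tempting and are not supported:
- A reader might infer that the mixed wording on other biologics is a second material error. The table row for [a] uses the same term as [b] and [c], and protocol Table 6 prohibits other biologics until Week 64, so the effect is probably small. It is a matter of alignment.
- A reader might treat a mismatch with the zero-exacerbation count in SAP 4.2.2.4 as proof of the fault. Cell [b] creates such mismatches by design, because non-completers and biologic starters without an exacerbation are failures. The mismatch alone diagnoses nothing.

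**Conclusion.** The rule is wrong as written for the three Week 28 exacerbation-free proportions: the definition says 28 weeks, but the derivation counts to Visit 15 or, at the primary lock, to the data cut-off. The error can only lower these proportions, by an amount that depends on enrolment date. Under the stated assumptions the loss is 5.7 to 18.5 points for any exacerbation at 0.4 to 1.0 per year, and 1.1 to 3.6 points for hospitalisation-type events at 0.05 to 0.10 per year. The first exceeds the sampling margin in most of the cases shown; the second is about the size of it. These figures are illustrations and not predictions.

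A reader might infer that the sponsor meant to use a longer window or that reported Week 28 results are wrong. The documents support neither: the surrounding text points to 28 weeks, and they do not show how the rule was programmed. Week 52 proportions, the annualised exacerbation rates and the primary endpoints are not affected. The change should be made.

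**What to change.** In SAP 4.2.4.2, including the closing paragraph on the hospitalisation/ER versions:

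1. For the Week 28 analysis, count only exacerbations and other-biologic initiations that start from first IP dose up to the Visit 9 date. If Visit 9 is not available, count up to first IP dose + 196 + 5 days or the end of available exacerbation follow-up, whichever is earlier.
2. Use this one window in [a] to [d], in both prose and table.
3. Keep completion separate from counting. Completion of 28 weeks is still judged by whether the planned treatment period under 3.3.1.1 exceeds 191 days.
4. Leave the Week 52 rule and the 3.3.1.1 definition unchanged.

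Points 3 and 4 matter. Ending the 3.3.1.1 period at Visit 9 while keeping the 191-day threshold would fail a participant whose Visit 9 fell on Days 183 to 191, inside the Table 3 window for Week 28, and who then stayed in the study. With the tests kept apart, an early or missing Visit 9 does not by itself make a continuing participant a non-completer.

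The cost is SAP wording and the matching program specification. No new data, visits or sample size are needed.
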